12.3. Audit

An audit of one or more participating study sites may be performed independently of, and separately from, routine monitoring to evaluate clinical study conduct and compliance with the protocol, SOPs, GCP, and the applicable regulatory requirements.

13. DATA HANDLING AND RECORD KEEPING

13.1. Data Management

13.1.1. Case Report Forms

An eCRF must be completed for each subject screened/enrolled in this study. These forms will be used to transmit information collected during the study to the Sponsor and regulatory authorities, as applicable.

The documentation related to the validation of the eCRFs will be maintained in the Trial Master File (TMF). The TMF will be maintained by the CRO and the Sponsor.

The Investigator will document subject data in his/her own subject files. These subject files will serve as source data for the study. All eCRF data required by this protocol will be recorded by study site personnel. All data entered into the eCRF will be supported by source documentation.

The Investigator or an authorized member of the Investigator's staff will make any necessary corrections to the eCRF. All changed information, including the date and person performing the corrections, will be available via the audit trail, which will be part of the electronic data capture system. For any correction, a reason for the alteration will be provided. The eCRFs will be reviewed periodically for completeness and acceptability by Sponsor personnel (or their representatives). The Sponsor (or their representatives) will also be allowed access to all source documents pertinent to the study in order to verify eCRF entries. The Investigator will review the eCRFs for completeness and accuracy and provide his or her electronic signature and date to the eCRFs as evidence thereof.

13.1.2. Source Documents

Per regulatory requirements, the Investigator or designee will maintain accurate and up-to-date study documentation, including source documentation for each study subject. Source documents are defined as original documents, data, and records. These may include, but are not limited to, hospital records, clinical and office charts, endoscopy reports, laboratory data/information, subjects' eDiaries or evaluation checklists, pharmacy dispensing and other records, recorded data from automated instruments, ECGs, X-rays, ultrasounds, right heart catheterization reports, echocardiograms. Data collected during this study must be recorded on the appropriate source documents.

The Investigator(s)/institution(s) will permit study-related monitoring, audits, IRB/IEC review, and regulatory inspection(s) and will provide direct access to the source data.

13.2. Study Documentation and Records Retention

The Investigator and study staff have the responsibility of maintaining a comprehensive and centralized filing system containing all study-related documentation. These files must be available for inspection by the Sponsor, representatives of the Sponsor, the IRB/IEC, and regulatory authorities (ie, FDA or international regulatory authorities) at any time, and should consist of the following elements:

- Subject files: containing the completed eCRFs (if applicable), supporting source documentation including medical records, laboratory data, and signed ICFs
- Regulatory files: containing the protocol with all amendments and Investigator signature pages, copies of all other regulatory documentation, all correspondence between the study site and the IRB/IEC and Sponsor, and drug accountability files, including a complete account of the receipt and disposition of the study treatment.

Records are to be available for 2 years after the last marketing application approval, or if the application is not approved or never submitted, 2 years after the appropriate regulatory authorities have been notified of the discontinuation of clinical development of the investigational product. The Sponsor will provide written notification when it is appropriate for the Investigator to discard the study-specific documents referenced above.

During the record retention period, the Investigator or designee must inform the Sponsor or designee (eg, CRO), of the following:

- Location of study documentation
- If the custody of documentation will be transferred or moved to another location
- If the Investigator is unable to retain documentation for the specified period

13.2.1. Clinical Study Site

Materials to be retained:

The head of clinical study site shall retain records, including documents and data, which relate to clinical study in accordance with ICH guideline for Good Clinical Practice (GCP) and Japan-GCP (J-GCP).

Retention period:

The head of clinical study sites shall retain records for a required period in accordance with ICH-GCP and J-GCP. However, the Investigator/the study center must arrange for retention of study records at the study center for at least 2 years after the last marketing application approval, or if the application is not approved or never submitted, 2 years after the appropriate regulatory authorities have been notified of the discontinuation of clinical development of the investigational product. The Sponsor will provide written notification when it is appropriate for the Investigator to discard the study specific documents referenced above. A record keeping manager shall be designated in retaining each record.

13.2.2. Principal Investigator

The Principal Investigator shall retain records, including documents and data, which relate to the clinical study in accordance with instruction from the head of the clinical study site.

13.2.3. Institutional Review Board (IRB)

Materials to be retained:

The person who establishes the IRB shall retain records, including documents and data, which relate to the clinical study in accordance with ICH-GCP and J-GCP.

Retention period:

The person who establishes the IRB shall retain records for required period in accordance with ICH-GCP and J-GCP. However, if the Sponsor requests to retain records longer than described, the person who establishes the IRB will discuss retention period and method with the Sponsor.

13.2.4. Sponsor and ICCC

Materials to be retained:

Sponsor and ICCC shall retain records, including documents and data, which relate to the clinical study in accordance with ICH-GCP and Japan GCP (J-GCP).

Retention period:

The Sponsor and the ICCC shall retain records for required period in accordance with ICH-GCP and J-GCP.

13.3. Clinical Study Report

Whether the study is completed or prematurely terminated, a clinical study report will be prepared and provided to the regulatory agencies according to applicable regulatory requirement(s).

13.4. Disclosure of Study Results

The Sponsor will post the results of the study in a publicly accessible database in accordance with the applicable laws and regulations.

14. **RESPONSIBILITIES**

14.1. Investigator Responsibilities

The Investigator must comply with this protocol and the conduct of all study procedures. The Investigator will disclose to the Sponsor sufficient, accurate, financial information to allow the Sponsor to submit accurate disclosure statements to the FDA per 21 Code of Federal Regulations (CFR) Part 54 (Financial Disclosure by Clinical Investigators). The Investigator is responsible for compliance with applicable sections of 21 CFR Part 312, Subpart D, (Responsibilities of Investigators) and other ICH GCP requirements, federal, and local laws, applicable to conducting drug studies.

The Investigator is responsible for ensuring an investigation is conducted according to the signed Investigator statement, the investigational plan, and applicable regulations; for protecting the rights, safety, and welfare of subjects under the Investigator's care; and for the control of drugs under investigation. An Investigator will, in accordance with the provisions of 21 CFR Part 50, obtain the informed consent of each human subject to whom the drug is administered.

14.2. Sponsor Responsibilities

The Sponsor is responsible for compliance with applicable sections of 21 CFR Part 312, Subpart D (Responsibilities of Sponsors). The Sponsor is responsible for selecting qualified Investigators, providing them with the information they need to conduct an investigation properly, ensuring proper monitoring of the investigation(s), ensuring the investigation(s) is conducted in accordance with the general investigational plan and protocols contained in the Investigational New Drug (IND) application, maintaining an effective IND with respect to the investigators, and ensuring the FDA, other applicable health authorities, and all participating Investigators are promptly informed of significant new adverse effects or risks with respect to the drug.

16. APPENDICES

APPENDIX 1: SCHEDULE OF ASSESSMENTS

Table 7: Schedule of Assessments

Visit Label (Based on Continuation from Study APD334-302)	W12/ D85 ^a ± 7 Days	W16/ D113 ± 7 Days	W20/ D141 ± 7 Days	W24/ D169 ± 7 Days	W32/ D225 ± 7 Days	W40/ D281 ± 7 Days	W48/ D337 ± 7 Days	W52/D365 / Early Termination ^b ± 7 Days	2-Week Follow-Up Visit ^c ± 3 Days	4-Week Follow-Up Visit ^c ± 3 Days
Evaluation		1	l	l	l					
Informed consent	X									
Inclusion/exclusion criteria	X									
eDiary review ^d		X	X	X	X	X	X	X		
MMSe								X		
Stool frequency and rectal bleeding subscore ^f		X	X	X	X	X	X	X		
PGA for total Mayo Clinic Score								X		
IBDQ, UC-PRO/SS, SF-36, WPAI-UC, and pain and urgency NRS								X		
Adverse event assessment		X	X	X	X	X	X	X	X	X
Vital signs ^g		X	X	X	X	X	X	X	X	X
12-lead ECG								X		
Physical examination ^h		X	X	X	X	X	X	X	X	X
Extraintestinal manifestations ⁱ								X	X	X
Pulmonary function test ^j					X			X	X	
Ophthalmoscopy with OCTk								X	X	
Pregnancy test ¹		X	X	X	X	X	X	X		X
CBC with differential and platelets		X	X	X	X	X	X	X	X	X
CD4 T-cell count		X	X	X	X	X	X	X	X	X

Visit Label (Based on Continuation from Study APD334-302)	W12/ D85 ^a ± 7 Days	W16/ D113 ± 7 Days	W20/ D141 ± 7 Days	W24/ D169 ± 7 Days	W32/ D225 ± 7 Days	W40/ D281 ± 7 Days	W48/ D337 ± 7 Days	W52/D365 / Early Termination ^b ± 7 Days	2-Week Follow-Up Visit ^c ± 3 Days	4-Week Follow-Up Visit ^c ± 3 Days
Evaluation		·	I	·	·	•	·		l	
Laboratory tests including hs-CRP ^m		X	X	X	X	X	X	X	X	
Stool sample/fecal calprotectin ⁿ				X				X		
Stool sample for microbiome								X		
Flexible proctosigmoidoscopy/ colonoscopy and biopsy °								X		
PK assessments ^p		X	X	X	X	X	X	X	X	X
Biomarkers blood sample ^q								X		
Concomitant medications and procedures ^r		X	X	X	X	X	X	X	X	X
Tuberculosis questionnaires		X	X	X	X	X	X	X	X	X
Tuberculosis tests								X		
Drug dispensation/accountability ^t	X	X	X	X	X	X	X	X		
Study treatment administration ^u	Once daily 12 week Study APD224 202. The Week 12 visit of Study APD224 202 sources as the Day 1 visit of this study.									

^a Subjects are continuing treatment from 12-week Study APD334-302. The Week 12 visit of Study APD334-302 serves as the Day 1 visit of this study. Subjects will be reconsented for this study. Screening for eligibility will be performed for Study APD334-302 and only modified eligibility criteria will be assessed for this study (Section 4.1 and Section 4.2). Visit labels and windows are relative to Week 0/Day 1 of Study APD334-302.

b Subjects discontinuing treatment prior to Week 52/Day 365 should have an Early Termination visit within 7 days of the last study treatment administration and before initiation of any new treatments. If a subject discontinues at or before Week 16, a sigmoidoscopy and biopsy are not required. For subjects with worsening disease or who complete Week 52 and wish to enter the APD334-303 OLE study, the Week 52/Early Termination visit will be used to assess eligibility for the OLE study.

^c For subjects discontinuing study treatment, 2-Week and 4-Week Follow-Up visits should be scheduled 2 weeks and 4 weeks after the Week 52/Early Termination visit and the indicated assessments performed; however, if the Early Termination or Week 52 visit is ≥ 2 weeks after the last dose of study treatment, the 2-Week Follow-Up visit is not required; however, the 4-Week Follow-Up visit should be scheduled and completed. If the Early Termination or Week 52 visit is ≥ 4 weeks after the last dose of study treatment, the 4-Week Follow-Up visit is not required. If the absolute peripheral lymphocyte count is not within normal limits at the 4-Week Follow-Up visit, subjects should return for CBC with differential according to local standard of care (captured as subsequent Follow-Up visit or unscheduled visit).

d Subjects will continue eDiary entries through the Eligibility Visit and during the treatment period. The subject eDiary will be reviewed by study site staff at each treatment visit.

^e The Week 52 MMS will be calculated using the Week 52 proctosigmoidoscopy and SF and RB scores completed by the subject 7 days prior to the visit using the 3 most recent consecutive days prior to the actual day of the study visit excluding the day of bowel preparation.

- f Stool frequency and RB subject-reported outcomes recorded daily using eDiary. The RB and SF subscores will be calculated as indicated in Section 9.7.1.
- g Safety vital signs will include resting heart rate and systolic and diastolic BP with subjects in the sitting position taken before dosing. Safety monitoring (Section 9.4.1) should be performed if a subject has had a dose interruption ≥ 7 consecutive days.
- h At Week 52, a complete physical examination (including assessments of the skin, head, eyes, ears, nose, throat, neck, thyroid, lungs, heart, abdomen, back, lymph nodes, extremities, and body weight) should be performed. All other visits should have a focused (complaints, signs, and symptoms) physical examination.
- During the specified full physical examination, specific systems (eyes, liver, skin, and joints) will be examined for EIMs.
- J Pulmonary function tests will include FEV₁ and FVC measurements. Where locally available, DLCO measurements will also be performed (sites where DLCO is not available should consult the Sponsor or Sponsor's delegate). The Week 32 assessment is only required for subjects with a history of mild pulmonary disease (eg, asthma, chronic obstructive pulmonary disease). The 2-Week Follow-Up visit assessment is only required if results from the Week 52/Early Termination visit are abnormal. Details regarding additional PFTs are provided in Section 9.8.4.
- k Details regarding ophthalmoscopy and OCT assessments are provided in Section 9.8.5. The 2-Week Follow-Up visit assessment is only required if results from the Week 52/Early Termination visit are abnormal.
- ¹ Urine pregnancy test for women of childbearing potential. A monthly home pregnancy test in non-visit months should be performed and any positive result immediately reported to the study site and a serum pregnancy test performed for confirmation. If home pregnancy test is not available, the pregnancy test will be performed on site during an unscheduled visit.
- m Clinical laboratory tests will include serum chemistry, hematology (including coagulation), urinalysis, and hs-CRP and should be obtained prior to the daily dosing.
- ⁿ Stool sample is for fecal calprotectin (all indicated visits) and bacterial culture, ova, and parasite evaluation for *C. difficile* assay at any point in the study when a subject becomes symptomatic, including worsening or return of disease activity.
- o To be read by a blinded central reader. If the Early Termination visit is within 4 weeks of the last sigmoidoscopy and biopsy, these procedures do not need to be repeated.
- P Pharmacokinetic blood samples are to be collected predose (within the 60-minute period prior to dosing). A PK sample should be taken, if possible, at the time of any SAE or AE leading to study treatment discontinuation. In addition, for subjects not enrolling into the APD334-303 study, a blood sample for PK should be drawn at the 2-Week and 4-Week Follow-Up visits. For all PK blood draws, the time of the last dose should be documented.
- 4 Blood samples for biomarkers should be collected on the indicated day prior to the daily dose as applicable.
- ^r All concomitant medications and procedures should be collected through the safety reporting period (Section 6.7). For subjects who received corticosteroid therapy during the APD334-302 study, corticosteroids should be tapered entering this study (Section 6.7.2.2).
- S QuantiFERON TB Gold and tuberculin skin test should not be performed in subjects previously diagnosed with TB infection. The TB questionnaire will be completed at every study visit for subjects receiving TB prophylaxis therapy.
- ^t Study treatment should be dispensed as indicated. For subjects who consent and are eligible for the APD334-303 OLE study prior to Week 52, double-blinded study treatment may be dispensed in the event there is a gap between the last on treatment visit of Study APD334-308 and W0/D1 of the OLE. Study treatment may be dispensed at Week 52 if the subject qualifies for and has opted to participate in the APD334-303 OLE study but who do not enter the OLE study on the same day as their Week 52 visit.
- ^u On days with scheduled study visits, subjects should not take their dose of study treatment at home in order to complete predose study procedures. The dose will be taken at the study site after all predose assessments and procedures have been completed. At the Week 12 visit, subjects should take study treatment after confirmation of eligibility and enrollment into Study APD334-308.

BP, blood pressure; CBC, complete blood count; D, day; DLCO, diffusing capacity of the lungs for carbon monoxide; ECG, electrocardiogram; eDiary, electronic diary; EIM, extraintestinal manifestations; FEV₁, forced expiratory volume at 1 second; FVC, forced vital capacity; hs-CRP, high-sensitivity C-reactive protein; IBDQ, Inflammatory Bowel Disease Questionnaire; MMS, modified Mayo score; NRS, numeric rating scale; OCT, optical coherence tomography; OLE, open-label extension; PGA, Physicians Global Assessment; PK, pharmacokinetics; RB, rectal bleeding; SAE, serious adverse event; SF, stool frequency; SF-36, Medical Outcomes Study 36-Item Short Form Health Survey; TB, tuberculosis; UC, ulcerative colitis; UC-PRO/SS, Ulcerative Colitis Patient-Reported Outcomes Signs and Symptoms; W, week; WPAI-UC, Work Productivity and Activity Impairment Questionnaire – Ulcerative Colitis

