3. INVESTIGATIONAL PLAN

3.1. Summary of Study Design

[figure not shown]
This is a multicenter, double-blind, placebo-controlled extension study of APD334-302 (12-week, randomized, double-blind, placebo-controlled induction study) to evaluate the efficacy and safety of etrasimod 2 mg in Japanese subjects with moderately to severely active UC. The study consists of a 40-Week Treatment Period and a 4-Week Follow-Up Period (Figure 2).

Japanese subjects who completed the Week 12 visit of Study APD334-302 are eligible for this study. The Week 12 visit of Study APD334-302 serves as the Day 1 visit of this study. Subjects will continue with the same blinded treatment assigned in Study APD334-302 for a total treatment duration of 52 weeks (12 weeks in Study APD334-302 plus 40 weeks in Study APD334-308).

Disease worsening will be monitored by Investigators through the treatment period. Subjects who either experience disease worsening or complete all study procedures at Week 52 will have the option to enroll into the APD334-303 OLE study if they meet all eligibility criteria.

Subjects who discontinue from the study and do not participate in the OLE study will have 2-Week and 4-Week Follow-Up visits after the last on-treatment visit/Early Termination visit (Table 7).

Figure 2: Study Design

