Because transient fluctuations of ALT or AST are common, and progression to severe drug-induced liver injury or acute liver failure is uncommon, automatic discontinuation of study treatment upon finding a greater than 3 × ULN elevation of ALT or AST may be unnecessary.

Subjects who discontinue treatment prematurely, regardless of the reason, should be instructed to return for an Early Termination visit within 7 days of the last study treatment administration (Table 7) and before initiation of any new treatments to complete all of the early termination assessments. If a subject discontinues due to pregnancy, they are not required to complete the endoscopy. If the Early Termination visit is within 4 weeks of the last sigmoidoscopy and biopsy, these procedures do not need to be repeated.

If the Early Termination visit is ≥ 2 weeks of the last dose of study treatment, the 2-Week Follow-Up visit is not required; however, the 4-Week Follow-Up visit should be scheduled and completed. If the Early Termination visit is ≥ 4 weeks of the last dose of study treatment, the 4-Week Follow-Up visit is not required unless the absolute lymphocyte count (ALC) is not within normal limits.

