9.5. Follow-Up Period

For subjects not participating in the OLE study, a follow-up visit will be performed at 2 and 4 weeks after the last dose of study treatment as indicated in the Schedule of Assessments (Table 7).

If the Early Termination or Study Completion visit is ≥ 2 weeks after the last dose of study treatment, the 2-Week Follow-Up visit is not required; however, the 4-Week Follow-Up visit should be scheduled and completed. If the Early Termination or Study Completion visit is ≥ 4 weeks after the last dose of study treatment, the 4-Week Follow-Up visit is not required.

If the absolute peripheral lymphocyte count is not within normal limits at the 4-Week Follow-Up visit, subjects should return for complete blood count (CBC) with differential according to local standard of care (captured as subsequent follow-up visit or unscheduled visit).

All adverse events should be recorded for 30 days after last dose of study treatment (Section 9.8.8.2.2).

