9.8.8.2.2. Recording Adverse Events

The adverse event reporting period for safety surveillance begins when the subject is initially included in the study (date of first signature of informed consent) and continues up to 30 days after the last study treatment administration. If an adverse event is not resolved or stabilized by this time, the Sponsor in consultation with the Investigator will decide whether to continue to monitor the adverse event or closeout the event in the database if no further follow-up is necessary.

Any SAE suspected to be related to the study treatment must be reported whenever it occurs, irrespective of the time elapsed since the last administration.

Investigators and study personnel will record all adverse events and SAEs whether received through an unsolicited report by a subject, elicited during subject questioning, discovered during physical examination, laboratory testing, and/or other means by recording them on the eCRF and/or SAE Form, as appropriate. The following information should be recorded on the adverse event eCRF:

- Description including onset and resolution dates
- Whether it met SAE criteria
- Severity
- Relationship to study treatment or other causality
- Outcome

For SAEs, events occurring secondary to the primary event should be described on the eCRF in the narrative description field.

The following should be considered when recording SAEs:

- Death is an outcome of an event. The event that resulted in the death should be recorded and reported on the eCRF.
- For hospitalizations, surgical, or diagnostic procedures, the illness leading to the surgical or diagnostic procedure should be recorded as the SAE, not the procedure itself. The procedure should be captured in the narrative as part of the action taken in response to the illness.

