For cardiac remonitoring upon treatment reinitiation after Day 2, as manifested by more than 1 timed measurement in vital signs or electrocardiogram (ECG) parameters on the same collection date of an unscheduled visit, measurement will be mapped to analysis visit of Cardiac Remonitoring 1, Cardiac Remonitoring 2, etc. in the respective analysis dataset. For analysis, each timed measurement will be programmatically assigned to the nearest hourly timepoint (e.g., Predose, 1-hour Postdose) based on their relationship to the dosing time on the same day. If the dosing date/time on the same day is missing, the timepoint will remain missing. Once mapped, these timed measurements from cardiac remonitoring visits will not be considered for any other analysis visit.

Windowing will be applied prior to any missing data calculations. The last non-missing measurement taken prior to Day 1 (including unscheduled assessments) will be labeled as “Baseline”. Unless stated otherwise, data from all visits including scheduled, unscheduled, and ET visits will be eligible for allocation to an analysis visit. The 2-Week and 4-Week Follow-Up visits will not be included in the visit windows and will be summarized separately without any window applied.

If one or more results for a variable are assigned to the same analysis visit, the result with the date closest to the protocol scheduled day will be used in the analysis, except for component subscores of MMS or TMS, in which case, the composite score and component subscores from the same date will be used in the analysis. If 2 measurements in the same analysis visit window are equidistant from the protocol scheduled study day, the earliest measurement will be used in the analysis. If multiple assessments are available on the same day, then the average of the assessment will be used in the analysis, except for laboratory and ECG data where the

assessment at the earliest time of the same day will be used. If both central and local assessments of the same ECG or lab test are available on the same day, the central result will take precedence over the local result.

For the overlapping visit windows at Week 48 and Week 52, Week 52 will take priority.

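### Follow-up visits are timed from the last dose in Section 9.5 but from the Week 52/Early Termination visit in Table 7, the lymphocyte exception to the 4-Week waiver differs between sections, and the 2-Week waiver removes the slot for a repeat PFT or OCT

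*Protocol*

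**What the plan says.** **Anchor.** Protocol Section 9.5 states that "a follow-up visit will be performed at 2 and 4 weeks after the last dose of study treatment". Table 7 footnote c (Appendix 1) states that "2-Week and 4-Week Follow-Up visits should be scheduled 2 weeks and 4 weeks after the Week 52/Early Termination visit". The synopsis and Section 3.1 side with the footnote: subjects "will have 2-Week and 4-Week Follow-Up visits after the last on-treatment visit/Early Termination visit". Both follow-up columns of Table 7 carry a window of ± 3 days.

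**Waivers.** Sections 5.1 and 9.5 and footnote c all drop the 2-Week visit when ET is 2 weeks or more after the last dose. All three also drop the 4-Week visit when that interval is 4 weeks or more, but Section 5.1 adds a condition: "the 4-Week Follow-Up visit is not required unless the absolute lymphocyte count (ALC) is not within normal limits". Section 9.5 and footnote c have no such condition. Both ask for a repeat blood count only if the lymphocyte count is abnormal at the 4-Week visit itself.

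**Repeat tests.** Of PFT and OCT, footnotes j and k of Table 7 each say: "The 2-Week Follow-Up visit assessment is only required if results from the Week 52/Early Termination visit are abnormal". The 4-Week column has no entry for either test.

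**Analysis.** SAP Section 6.4 states: "The 2-Week and 4-Week Follow-Up visits will not be included in the visit windows and will be summarized separately without any window applied". SAP Section 18.3.1 tabulates lymphocyte shifts from end of treatment to each follow-up visit, and Section 20 summarizes plasma concentration by time and treatment group.

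**The concern.** Protocol Section 3.2 gives these visits one purpose, to provide safety information off treatment. Time off drug is therefore the scale on which their results are read. If sites follow different sections, one visit label covers different times off drug, and the SAP applies no window that would separate them.

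Footnote c also mixes two clocks. It schedules from the ET visit but waives by time since the last dose.

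The difference over ALC decides whether a subject with an abnormal count has a further scheduled visit. The repeat PFT and OCT raise a related question, because a planned recheck can lose the only visit to which it is attached.

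**Working it through.** There is no plan figure to reproduce; the check is day arithmetic and a comparison of sections.

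**Inputs.** Let d be the number of days from last dose to the ET (or Week 52) visit. ET is due within 7 days of the last dose (Section 5.1 and footnote b), so d = 0 to 7 is compliant. The window is ± 3 days (Table 7). I assume that it applies under either anchor.

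**Formulas, in days off drug.**
- Section 9.5: 14 ± 3 = 11-17, and 28 ± 3 = 25-31, whatever d is.
- Footnote c: d + 14 ± 3, and d + 28 ± 3.

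| d | 2-Week visit, footnote c | 4-Week visit, footnote c |
|---|---|---|
| 0-7 (on time) | 0+11 to 7+17 = 11-24 | 0+25 to 7+31 = 25-38 |
| 8-13 (late) | 8+11 to 13+17 = 19-30 | 8+25 to 13+31 = 33-44 |
| 14-27 (late) | waived | 14+25 to 27+31 = 39-58 |
| 28 or more (late) | waived | waived (Section 5.1: kept if ALC abnormal) |

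**Can a site satisfy both anchors?** The 2-Week windows overlap when d + 11 ≤ 17, that is, when d ≤ 6. The 4-Week windows overlap when d + 25 ≤ 31, again d ≤ 6. At d = 7, still compliant, footnote c gives 18-24 and 32-38. Neither range shares a day with 11-17 or 25-31.

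**The mixed clock.** Under footnote c, d = 27 leads to a 4-Week visit nominally on day 27 + 28 = 55, while d = 28 leads to none.

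**ALC exception, at d ≥ 28.** Under Section 5.1 an abnormal ALC keeps the 4-Week visit. Under Section 9.5 and footnote c the visit is waived, and the rule for a repeat count cannot operate because its trigger is a result from the waived visit. The two issues also interact: if Section 5.1 keeps the visit but Section 9.5 dates it, the 25-31 day window has closed once d exceeds 31.

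**PFT and OCT, at d ≥ 14.** The 2-Week visit is waived under all three texts. Footnotes j and k attach the repeat to that visit, and the 4-Week column has neither test. The slot in the schedule is gone.

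**The case against.** The strongest reply is that this concerns few subjects and that other rules cover them. Much of that stands.

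- **Late visits.** Every waiver, and every range beyond 11-24 and 25-38, needs an ET visit after the 7-day limit or a Week 52 visit after a dosing gap. A reader might take days 39-58 as typical; they are not. The waiver text does, however, foresee such visits. For a completer dosed up to Week 52, the two anchors nearly coincide.
- **Other rechecks.** A reader might infer that abnormal results would go unexamined. The documents do not support that. Section 9.8.7 requires clinically significant laboratory abnormalities to be repeated, and under Table 6 an unblinded Medical Monitor reviews lymphocyte counts. Section 9.8.4 permits further PFTs and requires a follow-up visit after a fall below 50% of predicted. The copy reviewed lacks Sections 9.8.5 (OCT) and 9.7.4 (lymphopenia), so further rules may exist there. The laboratory backstop is partial: investigators are blinded to the counts, and the Monitor's instructions concern significant lymphopenia, a narrower trigger than a count outside normal limits.
- **Lymphocyte recovery.** A reader might infer that the recovery tables become unreadable. Section 1.3 reports return to about baseline within 7 days of the last dose, and every visit computed above falls on day 11 or later. Moving a visit from day 14 to day 21 does not carry it across the recovery period.
- **PK.** The time of the last dose is recorded for every PK draw (Table 7 footnote p), and the SAP listings give time since last dose. The steady-state trough and the concentration plots use Weeks 16 to 52 only. What remains exposed is the descriptive follow-up summary by label.

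None of this removes the difference in anchor or in the ALC exception.

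**Conclusion.** Two contradictions stand in the operative text: the visit anchor, and the ALC exception to the 4-Week waiver. For an on-time ET visit the anchor shifts the follow-up visits by up to 7 days, and at 7 days no date meets both versions. For ET on days 14-27, the 4-Week visit falls on days 39-58 instead of 25-31.

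The PFT and OCT point is separate and of a different kind. The waiver texts agree with one another; it is their common 2-Week waiver that does not fit footnotes j and k. The loss shown is of a scheduled slot, not of every possible recheck.

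A reader might also infer that the anchor conflict opens a gap in adverse event recording, because a visit on day 25 leaves 30 - 25 = 5 days before the period ends. That gap arises under Section 9.5 alone. Recording "continues up to 30 days after the last study treatment administration" under either anchor.

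The conclusion assumes the ± 3 day window under both anchors. The documents give no expected number of early terminators staying out of the open-label extension; the study plans about 35 subjects in all. No efficacy result is touched. The point is worth correcting because sites have two instructions and the labels conceal which was followed.

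**What to change.** **Protocol.** The sponsor should reconcile the synopsis, Sections 3.1, 5.1 and 9.5 and Table 7 footnote c so that one visit anchor and one ALC waiver rule apply throughout. The two should be settled together, since the anchor determines when a retained 4-Week visit could take place. The sponsor should also reconcile the 2-Week waiver with footnotes j and k. Which anchor, which ALC rule and which handling of the repeat tests is right is a clinical decision that this review does not make.

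**SAP.** In Sections 6.4, 18.3.1 and 20, add summaries of follow-up ALC and PK by actual days since last dose, alongside the visit label. Time since last dose is already listed for PK samples. For lymphocytes it follows from the collection date and the last-dose date that SAP Section 14.1 already uses.

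**Cost.** A protocol clarification and a few SAP sentences, with no new type of assessment or data item. If the follow-up visits are already complete, the SAP change alone would still show how far times off drug differ within each label.
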